### Screening Date

Screening date is defined as the date of screening assessment.

### Study Day 1

Day 1 is defined as the day that investigational product is administered to the subject.

### Study Day

Post day of dose: study day= (study date - date of study Day 1) +1

Pre day of dose: study day= (study date – date of study Day 1)

The day prior to the first investigational product dosing is Day -1 while the day of the first investigational product dose is Day 1.

### Concomitant Medications of Interest

The medications of interest are: nutritional vitamin D (vitamin D supplement), vitamin D sterol (active vitamin D), calcium supplements and phosphate binder as identified in the concomitant medication CRFs.

## **7. Analysis Subsets**

### **7.1 Safety Analysis Set**

The safety analysis set will consist of all subjects who receive at least 1 dose of investigational product.

### **7.2 Pharmacokinetic (PK) Concentration Analysis Set**

The pharmacokinetic (PK) concentration analysis set will contain all subjects who received investigational product and have at least one PK sample collected.

### **7.3 Subgroup Analyses**

No subgroup analysis is planned.

## **8. Interim Analysis and Early Stopping Guidelines**

No formal interim analysis is planned.

After 2 subjects in Cohort 1 complete the end of study visit, cumulative data will be reviewed prior to enrollment in Cohort 2 by a team composed of the Investigator(s), Amgen Medical Monitor, Amgen Global Safety Officer (GSO) or designee and additional members as needed (eg, Amgen Clinical Research Study Manager (CRSM), Biostatistician, PK Scientist, etc.). The voting members include the Principal Investigator or designee, Amgen Medical Monitor, and Amgen Global Safety Officer or designee. All available study data, including demographics, IP administration, medical history,

concomitant medications, adverse events, ECGs, vital signs, laboratory and PK results will be reviewed. Data review will not require that all queries be resolved or source verified. Cohort 2 will open for enrollment when the dose has been found to be reasonably tolerated based on available study data for at least 2 subjects enrolled in Cohort 1 and upon unanimous decision by the review committee. Based on emerging safety and PK data, the review committee may make other decisions (eg., lower the dose level, enroll additional subjects in Cohort 1, etc.).

## **9. Data Screening and Acceptance**

### **9.1 General Principles**

The objective of the data screening is to assess the quantity, quality, and statistical characteristics of the data relative to the requirements of the planned analyses.

### **9.2 Data Handling and Electronic Transfer of Data**

The Amgen Global Study Operations-Data Management (GSO-DM) department will provide all data to be used in the planned analyses. This study will use the RAVE database.

Details of PK, antibody and external lab data transfers to the data base are provided in the corresponding study data transfer plans. See details in the Data Management Plan (DMP).

An Analysis Dataset for PK Concentrations (ADPC) will be provided to Clinical Pharmacology, Modeling and Simulation (CPMS) from Biostatistics.

### **9.3 Handling of Missing and Incomplete Data**

The following imputation for missing or incomplete data will be performed if required:

- Incomplete or missing adverse event and concomitant medication dates will be imputed as described in [Appendix B](#). If imputed dates are used, then they will be identified as such in the final study report.
- PK concentrations below the lower limit of quantification will be omitted from PK parameter estimates.

### **9.4 Detection of Bias**

Lack of protocol compliance and the potential for biased statistical analyses will be examined by assessing the incidence of important protocol deviations. The clinical study team will identify and document the criteria for important protocol deviations.

### **9.5 Outliers**

All confirmed outlier data will be included in the analyses presented in this statistical analysis plan.

PK concentration data will be evaluated for outliers by visual inspection and decisions to re-assay individual samples will be made in accordance with standard CPMS practice. All excluded observations will be detailed by CPMS along with reasons for exclusion, in accordance with standard CPMS practices.

## **9.6 Distributional Characteristics**

Not applicable.

## **9.7 Validation of Statistical Analyses**

Programs will be developed and maintained, and output will be verified in accordance with current risk-based quality control procedures.

Tables, figures, and listings will be produced with validated standard macro programs where standard macros can produce the specified outputs.

The production environment for statistical analyses consists of Amgen-supported versions of statistical analysis software; for example, the SAS System version 9.2 or later.

## **10. Statistical Methods of Analysis**

### **10.1 General Principles**

Descriptive statistics will be provided for selected demographics, safety, PK, and PD data. Descriptive statistics on continuous measurements will include means, medians, standard deviations (SD), standard errors (SE), first and third quartiles and ranges, while categorical data will be summarized using frequency counts and percentages. Data will be summarized using the safety analysis set, unless otherwise specified, by cohorts.

When data are summarized by time, the values recorded against the scheduled time points listed in the protocol will be used. When assessing minimum/maximum increases or decreases over the study, all post-baseline assessments, including unscheduled assessments will be used.

### **10.2 Subject Accountability**

The number and percent of subjects who received investigational product, completed investigational product, discontinued from investigational product (including reasons for discontinuing), completed study, or discontinued the study (including reasons for discontinuing) will be summarized by cohort and overall. A table and a subject listing noting inclusion in each analysis subset will be provided for all subjects enrolled. A subject listing noting reason for discontinuation of treatment and reason for discontinuing the study will be provided.

### **10.3        Important Protocol Deviations**

Important Protocol Deviations (IPDs) categories are defined by the study team before the first subject's first visit and updated during the IPD reviews throughout the study prior to database lock. These definitions of IPD categories, sub-category codes, and descriptions will be used during the course of the study. Eligibility deviations are defined in the protocol.

The final IPD list will be used to produce the Summary of IPDs table and the list of subjects with IPDs. In addition, a separate listing of all inclusion and exclusion deviations will be provided.

### **10.4        Demographic and Baseline Characteristics**

Demographic (ie, age, sex, race and ethnicity), medical history, and baseline characteristics (ie, height, weight and BMI) will be summarized by cohorts and overall using descriptive statistics. If multiple races have been reported for a subject, the subject will be categorized as multiple.

A listing of the demographic and baseline characteristics will be provided. Listings of medical history will be provided.

### **10.5        Primary Endpoints**

#### **10.5.1        Common Adverse Events**

The Medical Dictionary for Regulatory Activities (MedDRA) version 18.1 or later will be used to code all events categorized as adverse events (AEs) to a system organ class and a preferred term. Determination of the severity of all adverse events (AE) will be consistent with Common Terminology Criteria for Adverse Events (CTCAE) version 4.0 unless specified otherwise.

Subject incidence of all common treatment-emergent adverse events will be tabulated by system organ class and preferred term by cohort and overall.

#### **10.5.2        Laboratory Test Results**

Hematology and chemistry data will be listed and reviewed for each subject. Values outside the normal laboratory reference range will be flagged as high or low on the listings. In addition, subject incidence of low corrected calcium (<7.0 mg/dL, <7.5 mg/dL, <8.0 mg/dL and <8.3 mg/dL) post-baseline will be provided. Summaries of key laboratory values [albumin corrected calcium (cCalcium), phosphorus, potassium, parathyroid hormone (PTH)] over time and changes from baseline over time will also be provided at each time point when samples are collected.

---

A summary of potential Hy's law cases meeting lab criteria will be provided. Subject incidence meeting the following criteria will be provided at baseline and post-baseline:

- 1) ALT or AST > 3 x ULN
- 2) Total bilirubin (TBL) > 2 x ULN
- 3) ALT or AST > 3 x ULN and TBL > 2 x ULN
- 4) ALT or AST > 3 x ULN and TBL > 2 x ULN and ALP < 2 x ULN

For post-baseline, if more than one value exist for a lab measure, the highest value will be used for these evaluations.

For subjects who meet the Hy's law lab criteria, information on their medical history and concomitant medication will be provided to further evaluate whether these are true Hy's law cases.

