**7. STUDY PROCEDURES**

**7.1 Schedule of Assessments**

**Table 1. Schedule of Assessments**

	Screening	Baseline		Treatment		Follow up			EOS	
Study Day	-14 to -3	-2		1		3	5 a	8	10	30
Study Time			0	10 min	4 hour					
General and Safety Assessments										
Informed consent	X									
Medical history	X									
Weight (kg)	X	X								X
Height (cm)	X									
Vital signs (BP, HR, Temp)	X	X								X
Physical examination	X									X
12-lead ECG	X	X								X
Serious adverse events			X-----X							
Adverse Events				X-----X						
Concomitant medications			X-----X							
Dosing										
Etelcalcetide administration b			X							
Laboratory Assessments										
Clinical chemistry	X									X
Hematology	X									X
Ionized Ca, Serum albumin, Serum cCa c, d	X	X			X	X		X	X	X
Serum PTH c	X	X			X	X		X	X	X
Serum pregnancy test (females of child bearing potential only) e	X									
Pharmacokinetic and Other Blood Samples										
Etelcalcetide PK plasma collection c, f			X	X	X f	X	X	X	X	X
Antibody sample collection g		X								X

Footnotes defined on next page of table

cCa = albumin-corrected calcium; EOS = End of Study; iCa = ionized calcium; HD = haemodialysis; IV = intravenous

- a. Subjects will continue to receive HD per their regular schedule (Day -2, 1, 3, 5 [or Day 6 depending on the day of the week the study begins], 8 and 10).
- b. On Day 1, etelcalcetide will be administered as an IV bolus dose after HD during rinse back.
- c. All procedures (except those scheduled on Day 1 at time 0, 10 min and 4 hour and Day 3 post-HD) will be performed prior to HD on the respective study day.
- d. Serum samples for albumin and calcium for screening and routine monitoring of pre-HD cCa. When albumin is less than 4.0 mg/dL, the calcium level will be corrected according to the formula:  $cCa \text{ (mg/dL)} = \text{total Ca (mg/dL)} + (4 - \text{albumin (g/dL)}) * 0.8$ .
- e. Pregnancy tests will be performed in female subjects of child-bearing potential within 7 days prior to start of investigational product.
- f. PK plasma collection pre-HD and post-HD on Day 3
- g. Subjects with positive titers for antibodies to etelcalcetide at EOS may be asked to return to the clinical research unit to provide additional serum samples.

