### Drug-induced Liver Injury Reporting & Additional Assessments

#### Reporting

To facilitate appropriate monitoring for signals of DILI, cases of concurrent AST or ALT and TBL and/or INR elevation according to the criteria specified in [Section 6.3](#) require the following:

- The event is to be reported to Amgen as a serious adverse event within 24 hours of discovery or notification of the event (ie, before additional etiologic investigations have been concluded)
- The appropriate CRF (eg, Event CRF) that captures information necessary to facilitate the evaluation of treatment-emergent liver abnormalities is to be completed and sent to the Amgen.

Other events of hepatotoxicity and potential DILI are to be reported as serious adverse events if they meet the criteria for a serious adverse event defined in [Section 9.2.2](#).

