#### Additional Clinical Assessments and Observation

All subjects in whom investigational product(s) or protocol-required therapies is/are withheld (either permanently or conditionally) due to potential DILI as specified in [Section 6.3](#) or who experience AST or ALT elevations  $> 3 \times$  ULN are to undergo a period of “close observation” until abnormalities return to normal or to the subject’s baseline levels. Assessments that are to be performed during this period include:

- Repeat AST, ALT, ALP, bilirubin (total and direct), and INR within 24 hours
- In cases of TBL  $> 2 \times$  ULN or INR  $> 1.5$ , retesting of liver tests, BIL (total and direct), and INR is to be performed every 24 hours until laboratory abnormalities improve
- Testing frequency of the above laboratory tests may decrease if the abnormalities stabilize or the investigational product(s) or protocol-required therapies has/have been discontinued AND the subject is asymptomatic.
- Initiate investigation of alternative causes for elevated AST or ALT and/or elevated TBL:
  - Obtain complete blood count (CBC) with differential to assess for eosinophilia
  - Obtain serum total immunoglobulin IgG, Anti-nuclear antibody (ANA), Anti Smooth Muscle Antibody, and Liver Kidney Microsomal antibody 1 (LKM1) to assess for autoimmune hepatitis

- Obtain serum acetaminophen (paracetamol) levels
- Obtain a more detailed history of:
  - Prior and/or concurrent diseases or illness
  - Exposure to environmental and/or industrial chemical agents
  - Symptoms (if applicable) including right upper quadrant pain, hypersensitivity-type reactions, fatigue, nausea, vomiting and fever
  - Prior and/or concurrent use of alcohol, recreational drugs and special diets
  - Concomitant use of medications (including non-prescription medicines and herbal and dietary supplements), plants, and mushrooms
- Obtain viral serologies
- Obtain CPK, haptoglobin, LDH, and peripheral blood smear
- Perform appropriate liver imaging if clinically indicated
- Obtain appropriate blood sampling for pharmacokinetic analysis if this has not already been collected
- Obtain hepatology consult (liver biopsy may be considered in consultation with an hepatologist)

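### In SAP 10.5.2 the highest-value rule runs the wrong way for ALP in Hy's law criterion 4, and it pairs peaks from different dates

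*SAP*

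**What the plan says.** SAP 10.5.2 plans a summary of potential Hy's law cases. Four criteria are counted: "Subject incidence meeting the following criteria will be provided at baseline and post-baseline". Criteria 1 and 2 each use a single condition (ALT or AST, then total bilirubin), and criterion 3 joins them. Criterion 4 adds a condition on ALP: "ALT or AST > 3 x ULN and TBL > 2 x ULN and ALP < 2 x ULN".

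Where a subject has several post-baseline values, the rule is: "For post-baseline, if more than one value exist for a lab measure, the highest value will be used for these evaluations". It covers all four criteria. It makes no exception for ALP and sets no condition on sample date.

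Two other statements in SAP 10.5.2 bear on the point. Individual data stay visible: "Hematology and chemistry data will be listed and reviewed for each subject". Flagged subjects get a further look: "For subjects who meet the Hy's law lab criteria, information on their medical history and concomitant medication will be provided".

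In the protocol, the "Clinical chemistry" row of Table 1 is marked only at screening and at the Day 30 end-of-study visit. Appendix A requires more testing after a liver signal: "Repeat AST, ALT, ALP, bilirubin (total and direct), and INR within 24 hours". If bilirubin exceeds 2 x ULN or INR exceeds 1.5, testing is then daily until values improve. The reporting part of Appendix A describes the signal as "cases of concurrent AST or ALT and TBL and/or INR elevation according to the criteria specified in" protocol Section 6.3.

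**The concern.** Taking the highest value is the cautious choice for a test that must be high. For a test that must be low it is the reverse: each further ALP result can leave criterion 4 as it was or defeat it, but can never help it to be met. The rule also lets the ALT or AST peak, the bilirubin peak and the ALP peak come from different dates, although the protocol speaks of concurrent elevation.

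At stake is the criterion 4 count, the most specific of the four. Repeat panels are ordered mainly in subjects with a liver signal, so the rule comes into play in the subjects whom the table is meant to describe.

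**Working it through.** The plan states no figure to reproduce, so this is a check of logic.

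**Inputs.** The four criteria and the value rule are from SAP 10.5.2. The number of scheduled post-dose chemistry panels is one (protocol Table 1, Day 30). Repeat panels follow protocol Appendix A. The laboratory values in the examples are assumptions, in multiples of ULN. I also assume that repeat results reach the analysis data. Appendix A asks for them in the CRF, and SAP 10.1 includes unscheduled values in minimum and maximum assessments.

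**Notation.** For draw j, let A be ALT or AST, T total bilirubin and P ALP.

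- SAP rule for criterion 4: max A > 3, max T > 2 and max P < 2, each maximum taken separately over all draws.
- Same-draw rule: at least one draw j has A_j > 3, T_j > 2 and P_j < 2.

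**Step 1: one draw.** Each maximum is the single value, so the two rules always agree. A subject with only the scheduled Day 30 panel is unaffected.

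**Step 2: several draws, direction of error.** Since max A ≥ A_j and max T ≥ T_j, any subject who meets criterion 1, 2 or 3 on some draw also meets it under the SAP rule. None of these three can lose a subject. For criteria 1 and 2, which involve no pairing across tests, the SAP rule gives the right answer. For ALP, max P < 2 requires every draw to be below 2, so one higher draw anywhere removes the subject from criterion 4. Pairing separate maxima can add subjects to criteria 3 and 4.

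**Step 3: worked subjects.**

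| Example | Day | ALT | TBL | ALP | Criterion 4 on this draw |
|---|---|---|---|---|---|
| A | 30 | 5 | 2.5 | 1.5 | met |
| A | 31 | 4.5 | 2.6 | 1.8 | met |
| A | 34 | 2.5 | 2.2 | 2.3 | not met |
| A, SAP maxima | any | 5 | 2.6 | 2.3 | **not met** (2.3 is not < 2) |
| B | 30 | 4 | 1.2 | 1.0 | not met (1.2 is not > 2) |
| B | 37 | 1.5 | 2.4 | 1.2 | not met (1.5 is not > 3) |
| B, SAP maxima | any | 4 | 2.4 | 1.2 | **met** |

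Example A qualifies on two draws but is dropped from criterion 4. It remains under criterion 3 (5 > 3 and 2.6 > 2). Example B qualifies on no draw but is counted under criteria 3 and 4.

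**Step 4: check on arbitrary profiles.** Both rules were applied to 100,000 random profiles for each of 1, 2, 3 and 5 draws. With one draw there were 0 disagreements. With 2, 3 and 5 draws, criterion 4 was both lost and wrongly gained, and criterion 3 was never lost. How often each happened reflects the arbitrary value ranges, so it is not evidence on frequency.

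**Step 5: size if it happens.** At least 10 subjects are planned, at least 5 per cohort. At those minimum numbers, one reclassified subject moves the criterion 4 incidence by 1/10 = 10 percentage points overall, or 1/5 = 20 within a cohort. The documents give no figure for how likely such a subject is.

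**The case against.** The strongest reply is that little depends on this count, and most of that reply stands.

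- **Cases being missed.** A reader might infer that a genuine liver case could vanish. The documents do not support that. The table shows potential cases on laboratory criteria, with causality judged separately. The dropped subject stays under criterion 3 and in the listings. Protocol Section 6.3 and Appendix A define the event for serious adverse event reporting with no ALP condition.
- **Primary endpoint.** The summary sits under the SAP's primary-endpoint heading, so a reader might infer that a primary endpoint is affected. The key laboratory tests named in SAP 4.1 are corrected calcium, phosphorus, potassium and PTH, with no liver test among them.
- **Rarity.** This is a single-dose study that excludes screening ALT or AST at or above 1.5 x ULN and schedules one post-dose panel. Few subjects, if any, will have repeat panels. A probability for ALP crossing the limit would need an ALP level, its variability and the correlation between one child's serial values. The documents give none of these, so I offer no probability.
- **Peak pairing as a screen.** A reader might infer that criterion 3 must also use one date. Appendix A does not define concurrent as same-date, and pairing peaks is a defensible sensitive screen. A strict same-date rule would lose subjects whose bilirubin crosses its limit on a different draw from ALT.

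None of this defends taking the highest ALP for a criterion that needs ALP to be low. The planned review of flagged subjects does not cure it either: it supplies history and medication, not sample timing.

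**Conclusion.** The point holds for criterion 4. By its plain wording, the rule can reject a subject who meets the criterion on a single draw, and can accept one who meets it on none. The first error comes from using the highest ALP, the second from pairing peaks across dates. Criteria 1 and 2 are handled correctly. Criterion 3 can only gain subjects, which is acceptable if the table says so.

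The practical effect is limited to the few subjects with repeat panels, and safety reporting is untouched. The conclusion rests on the SAP wording and on repeat results entering the analysis; the example values show only that each error is possible. It is worth correcting before the analysis because the stated rule gives a wrong answer and the remedy is cheap.

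**What to change.** Reword the value rule in SAP 10.5.2 along these lines:

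- Criteria 1 and 2 use the highest post-baseline value.
- Criterion 4 is evaluated on values from the same draw, or within a stated short window, using the ALP from that draw. A subject is counted if any post-baseline draw qualifies.
- Criterion 3 may keep separate peaks if the table labels it a peak-value screen. Sample dates are shown for every flagged subject.

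The cost is a few sentences and a small programming change, with no new data. There is one trade-off: under a strict same-draw rule, criterion 4 can miss a subject whose panel on a given date is incomplete. A stated window reduces that risk.

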#### **10.5.3        Vital Signs**

Vital signs will be listed and reviewed for each subject. Summaries of heart rate, temperature and blood pressure data over time and change from baseline will be provided.

#### **10.5.4        Electrocardiogram (ECG)**

Summaries over time and/or changes from baseline over time will be provided for all ECG parameters including PR, QRS, QT, QTcF and QTcB.

Subjects will be categorized into the following groups per their maximum change from baseline in QTcF and QTcB. Unscheduled assessments will be included in the determination of the maximum change.

- <=30 msec
- >30 – 60 msec
- >60 msec

The number and percentage of subjects in each group will be summarized.

Subjects will also be categorized into the following groups per their maximum post-baseline QTcF and QTcB. Unscheduled assessments will be included in the determination of the maximum post baseline value.

- <=450 msec
- >450 – 480 msec
- >480 – 500 msec
- >500 msec

The number of subjects in each group will be summarized for each cohort. All on-study ECG data will be listed.

